APPENDIX L: CASE REPORT FORMS112
APPENDIX M: INVESTIGATIONAL PLAN REVISIONS.....113

LIST OF TABLES

Table 1. Follow-up Windows	26
Table 2. Data Collection Summary.....	27
Table 3. Unavoidable Events	38
Table 4. Heart Mate II Study Rates	44
Table 5. Study Oversight Contact Information.....	60
Table 6. Investigator Reporting Responsibility	68
Table 7. Sponsor Reporting Responsibility	70

TABLE OF FIGURES

Figure 1. Study Design Flowchart	17
Figure 2 Annual Survival versus Hospitalization versus NYHA	58

Trial Contact Information

Sponsor, Manufacturer & Distributor	Sunshine Heart, Inc. [name] Tele: [name] [contact] www.sunshineheart.com
-------------------------------------	---

Clinical/Technical Support [contact]-SHCPULSE)

INTRODUCTION

PURPOSE

Sunshine Heart is sponsoring a prospective, multi-center, randomized trial to assess the safety and efficacy of the C-Pulse® System (“C-Pulse”).

The purpose of the study is to determine whether the use of the C-Pulse as a treatment for patients in moderate to severe heart failure (HF) has demonstrated safety and efficacy, such that the C-Pulse System merits Food and Drug Administration (FDA) approval to market the device in the United States.

STUDY SIZE AND DURATION

This clinical study is anticipated to commence October 2012. The enrollment and 12 month follow-up duration of the study is expected to be 3.5 years. The primary study population will include 388 subjects enrolled and randomized in up to 40 centers in the United States (US) and potentially additional sites in Canada. The treatment group will include 194 subjects randomized to and implanted with C-Pulse® System and the control group will include 194 subjects randomized to and followed according to the same follow-up schedule as the treated subjects. All patients must be consented prior to performing any study related procedures. A patient is considered enrolled upon signing the informed consent. To minimize the burden to the patient, data collected as standard of care and not for the specific reason for study eligibility may be used for baseline data points as outlined in the informed consent. These tests will suffice for the baseline dataset if collected within the specified baseline data collection timeframe prior to implant. The subjects will be assigned a screening number upon signing the consent.

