Patients will be enrolled into the trial upon providing informed consent. Each subject will be randomized after meeting the Eligibility Criteria and completion of baseline testing. Due to time required for baseline testing and scheduling of implant, sites will manage these items within the 30 day window as suited for the individual institution and patient. Procedures related directly to the study must not be performed prior to informed consent. Data collection will be noted prior to implantation of the device and at six months following implant, then long term at 12 and 18 months followed by annually post-implant for five years. Serious adverse events (SAE) will be collected throughout the study until study closure and will be adjudicated by an independent Clinical Event Committee (CEC).

Progress reports of the clinical outcomes will be reviewed by the DSMB after randomization of forty (40) patients and at least twice annually based on study progress. A progress report will be sent to FDA for review as specified in the Statistical Methods and Data Analysis section.

The total duration of the study including the enrollment and 12 month follow-up is expected to be approximately 36-42 months.

OBJECTIVES

Primary Objectives

The primary objectives of the study are to demonstrate the safety and efficacy of the C-Pulse therapy as compared to OMT. Refer to the section on Statistical Methods and Data Analysis for a detailed discussion of the definitions and methodology.

1. Primary Efficacy Objective:

To demonstrate the superiority of the C-Pulse therapy in increasing survival free from worsening heart failure resulting in hospitalization, LVAD implantation, cardiac transplantation or death as compared to OMT.

2. Primary Safety Objective:

To demonstrate the safety of the C-Pulse System by evaluating freedom from serious adverse events that are adjudicated as definitely related to device, therapy or procedure and resulting in either surgical intervention or death.

Secondary Objectives

The secondary objectives are as follows:

1. To demonstrate the superiority of C-Pulse therapy as compared to the OMT Control in improvement in 6 Minute Hall Walk score at 12 months post-randomization.
2. To demonstrate the superiority of C-Pulse therapy as compared to the OMT Control in improvement in 6 Minute Hall Walk score at 18 months post-randomization.

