3. To demonstrate the superiority of C-Pulse therapy as compared to the OMT Control in improvement in LVEF at 12 months post-randomization.
4. To demonstrate the superiority of the C-Pulse therapy as compared to the OMT Control in improvement in the total days alive out of the hospital for worsening heart failure through 12 months post-randomization.
5. To demonstrate the superiority of the C-Pulse therapy as compared to the OMT Control in improvement in the total days alive out of the hospital through 12 months post-randomization.
6. To demonstrate the superiority of C-Pulse therapy as compared to the OMT Control in improvement in KCCQ scores at 12 months post-randomization.

PATIENT SELECTION

Inclusion Criteria

Patients of both genders who satisfy all inclusion and exclusion criteria are eligible for this clinical study. Patients must meet the following criteria:

1. Left ventricular ejection fraction (LVEF) $\leq 35\%$ (by transthoracic ECHO within 90 days prior to randomization)
2. ACC/AHA Stage C and NYHA III to ambulatory Class IV
3. Age ≥ 18 years
4. Must have cardiac resynchronization therapy (CRT) when clinically indicated, implanted ≥ 90 days prior to enrollment.
5. Must have an implanted cardio-defibrillator (ICD) when clinically indicated, implanted at least 30 days prior to enrollment.

Note: If a subject is clinically indicated for an ICD but refuses the ICD, he/she may be enrolled. Please document the refusal of the ICD in the medical record and the eCRFs.

6. Patient must be on stable, up-titrated medical therapy as recommended according to current guidelines (Circulation. 2009; 119 (12): 1977-2016) which minimally includes:
 - *ACE-inhibitor (ACE-I) at stable doses for 1 month prior to enrollment, if tolerated,*
AND
 - *a beta blocker (carvedilol, sustained release metoprolol succinate, or bisoprolol) for 3 months prior to enrollment, if tolerated, with a stable up-titrated dose for 1 month prior to enrollment.*
 - *This also includes an Angiotensin II Receptor Blocker (ARB) at stable doses for 1 month prior to enrollment, if tolerated, when ACE-I is not tolerated.*
 - *Stable is defined as no more than a 100% increase or a 50% decrease in dose. If the patient is intolerant to ACE-I, ARB, or beta blockers, documented evidence must be available.*

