In the event the subject becomes lost to follow-up, the investigational site should make two documented attempts to contact the subject. A Study Exit record must be completed and the subject will no longer be followed in the clinical study.

Data Collection Overview

A review of patient files is required to determine preliminary eligibility according to patient inclusion and exclusion criteria. Baseline data including functional tests must be collected no more than **30** days prior to randomization. Baseline imaging such as echo and CT scans must be collected no more than 90 days prior to randomization. See the data collection table for details.

Follow-up data will be collected at the time of implant, hospital discharge, at planned follow-ups (6 week, 3, 6, 12, 18-month and annually from the implant date thereafter up to 5 years). All serious adverse events will be collected throughout the study until closure.

All study subjects will follow the prescribed follow-up scheduled despite randomization. Day 0 for the treatment group will be the day of implant. Day 0 for the Control Group will be the day of randomization. Each group will continue with optimal medical therapy for the duration of the study, including all standard of care medications and treatments including transplant, VAD, etc. If the subjects are transplanted or placed on another device they will be censored from the primary endpoint analysis and study exited. Subjects implanted with the C-Pulse will be followed until device removal. If the PIL is explanted and not replaced, the subject will be followed for safety until removal of the entire system.

Data will be collected via electronic data capture (EDC) screens referred to as e-case report forms (eCRFs). Echocardiogram tapes and digital storage media must be documented in the patient medical record for source documentation.

Table 1, below outlines the data collection with the appropriate follow-up time windows.

Table 1. Follow-up Windows

Evaluation	Time Window
Pre-Implant Evaluation	No more than 30 days prior to implant
Randomization	Post Baseline Testing and Pre-Implant
Implant	Day 0 (Treatment Group) – Implant Day 0 (Control Group) – Randomization
Pre-Discharge	Within 36 hours prior to discharge
6 – week follow-up	Days 42 ± 7 Post-Implant
3 – month follow-up	Days 90 ± 14 Post-Implant
6 – month follow-up	Days 180 ± 30 Post-Implant
12 – month follow-up	Day 365 ± 30 Post-Implant
18 – month follow-up	Day 540 ± 30 Post-Implant

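### The 12- and 18-month visits run from implant in the device arm and from randomization in controls, while the four visit-based secondary objectives are all set at a time after randomization

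*Combined protocol and SAP*

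**What the plan says.** **Visit schedule.** The Data Collection Overview (under Procedures) states: "Day 0 for the treatment group will be the day of implant. Day 0 for the Control Group will be the day of randomization". Table 1 (Follow-up Windows) repeats this. It lists the 12-month visit as "Day 365 ± 30 Post-Implant" and the 18-month visit as "Day 540 ± 30 Post-Implant", and places randomization before implant.

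**Secondary objectives.** The list under Objectives names "improvement in 6 Minute Hall Walk score at 12 months post-randomization", "improvement in 6 Minute Hall Walk score at 18 months post-randomization" and "improvement in LVEF at 12 months post-randomization". It gives the same 12-month post-randomization timing for KCCQ. The fuller definitions under Secondary Efficacy Endpoints say only that these measures are taken at 12 or 18 months. They give the worst possible outcome to subjects not evaluated because of earlier VAD implant, transplant or death. The two days-alive-out-of-hospital endpoints are counted by date from randomization.

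**Wait for implant.** Patient Informed Consent and Enrollment caps the interval from consent to implant at 30 days.

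**Other endpoints.** The primary safety endpoint names implant as its origin. The primary efficacy endpoint section names none and refers to a Statistical Analysis Plan for its methods; no separate text of that plan was available for this review. Analysis Population keeps every randomized subject in the assigned arm for the primary analyses, implanted or not.

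**The concern.** Randomization comes before implant, so for any device subject who waits, month 12 has two dates: one in Table 1 and a different one in the objectives. No section says which applies. A site that follows Table 1 assesses the device arm later after randomization than the control arm, always in the same direction.

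The delay affects results through the worst-outcome rule. A later visit gives the device arm more time to lose subjects to death, VAD or transplant before assessment. The two six-minute-walk endpoints come first in the testing order, and the section on Type I error control tests the secondary objectives hierarchically as listed. Power lost on those two therefore limits everything below them.

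**Working it through.** **1. Visit windows after randomization.** For a wait of w days from randomization to implant, a device visit at day d after implant falls on day d + w after randomization. Controls have w = 0. The wait is at most 30 days if the consent-to-implant limit is kept. As an average, 30 days is a ceiling and not plausible, because the interval starts at consent and must also hold any post-consent baseline testing and Subject Eligibility Committee review. Waits of 7 and 14 days are assumptions.

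| Wait (days) | 12-month window | 18-month window |
|---|---|---|
| Controls, or 0 | 335–395 | 510–570 |
| 7 | 342–402 | 517–577 |
| 14 | 349–409 | 524–584 |
| 30 | 365–425 | 540–600 |

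Over all waits of 0 to 30 days the device arm spans 335–425 and 510–600.

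**2. Extra worst outcomes.** The sample-size justification takes 84% six-month survival from an outside study. That figure underlies the plan's own control rate: 64% + (100% − 84%)/2 = 72%, as stated. I assume a constant death hazard, equal in both arms: h = −ln(0.84)/0.5 = 0.349 per year.

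- Survival to day t: S(t) = exp(−h × t/365.25), so S(365) = 0.7058 and S(540) = 0.5972.
- Deaths by day 365 per arm with equal timing: 194 × (1 − 0.7058) = 57.1.
- Extra device deaths before the 12-month visit: 194 × [S(365) − S(365 + w)].
 - w = 7: 194 × (0.7058 − 0.7011) = 0.9
 - w = 14: 194 × (0.7058 − 0.6964) = 1.8
 - w = 30: 194 × (0.7058 − 0.6858) = 3.9
- The same formula at 18 months gives 0.8, 1.5 and 3.3.

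This counts deaths only. The plan gives no separate VAD or transplant rate, and those events would add to the total.

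**3. What that does to a rank test at 12 months.** The plan states no power for the secondary endpoints, so this is an illustration. Let sD and sC be the proportions alive at the visit in each arm, and δ the effect among survivors in SD units. Deaths rank below all survivors and are ordered by time of death, as in Handling of Missing Data. Let q be the chance that the device subject died later when both died. Then

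θ = sD·sC·Φ(δ/√2) + sD(1 − sC) + (1 − sD)(1 − sC)q, with SE ≈ √(1/(6 × 194)) = 0.0293 and power ≈ Φ((θ − 0.5)/SE − 1.96).

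δ = 0.6 is chosen only because it gives about 80% power at equal timing. Setting δ = 0 gives the chance of a false finding in the device's favor.

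| Wait (days) | sD | q | θ (δ = 0.6) | Power, formula | Power, simulated (20,000 runs) | One-sided false success, simulated |
|---|---|---|---|---|---|---|
| 0 | 0.7058 | 0.500 | 0.582 | 80% | 79.6% | 2.5% |
| 7 | 0.7011 | 0.508 | 0.580 | 78% | 77.3% | 2.1% |
| 14 | 0.6964 | 0.515 | 0.577 | 75% | 74.8% | 1.8% |
| 30 | 0.6858 | 0.532 | 0.573 | 70% | 69.1% | 1.4% |

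Power and false success both fall, so the shift is conservative with respect to the device.

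**The case against.** **The shift is small, and implant timing can be defended.** Timing visits from implant gives every device subject the same exposure at assessment. With a wait of 7 or 14 days the nominal device visit (day 372 or 379) still lies inside the control window of 335–395. The largest power loss needs a 30-day average wait, and the illustration rests on an effect chosen for convenience. All of this stands and limits the size of the point. It does not remove the contradiction.

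**The wording of the objectives could be changed instead.** That would make the text agree. It would leave the arms assessed at different times after randomization, with the unequal build-up of worst outcomes intact. It would also leave randomized device subjects who are never implanted without a date for month 12.

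**Stronger readings that the documents do not support.**

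- A reader might infer that the primary hazard ratio is also counted from Day 0 and is therefore biased. Day 0 is defined as part of the visit schedule and is never named as the primary endpoint's clock. The Statistical Analysis Plan may set that origin, and Analysis Population retains all randomized subjects as assigned, which fits a randomization origin better.
- A reader might infer that all six secondary endpoints are mistimed. The two days-alive endpoints are counted by date from randomization and do not depend on visits.
- A reader might see a further contradiction in the statement under Study Size and Duration that controls are "followed according to the same follow-up schedule as the treated subjects". The same visits apply relative to each arm's Day 0, so that sentence can stand.

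**Conclusion.** The conflict is real and confined to four endpoints: six-minute walk at 12 and 18 months, and LVEF and KCCQ at 12 months. Nothing in the text reviewed reconciles Table 1 with the Secondary Objectives.

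Its size is modest. At 12 months the device arm gains about 1 to 2 worst-outcome subjects of 194 for waits of 7 to 14 days, and 3.9 at the 30-day ceiling, on top of about 57 expected in each arm. These counts rest on assumed waits, on the outside study's 84% survival and on constant, equal hazards. The direction is against the device, so the sponsor bears the cost, as lost power on the endpoints tested first.

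On the primary efficacy endpoint the finding goes no further than this: its time origin is not named in the text reviewed and should be confirmed. The sample size of 388 is not in question. The correction should be made, but the point does not threaten the trial's main conclusion.

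**What to change.** 1. State that time zero for the primary and all secondary efficacy analyses is the date of randomization in both arms, including device subjects who are never implanted. State that events between randomization and implant count in the assigned arm, in line with Analysis Population. If the Statistical Analysis Plan already says so, a cross-reference is enough.
2. Keep implant as the origin for the primary safety endpoint only.
3. In Table 1, time the 12- and 18-month efficacy assessments from randomization in both arms, to match the Secondary Objectives.

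**Cost.** This is wording and visit-window programming. Event capture need not change: "All serious adverse events will be collected throughout the study until closure".

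- Device subjects would be assessed after up to 30 days less device exposure.
- If the post-implant window is also kept, one visit must satisfy both rules. For a wait of w days the joint window runs from day 335 + w to 395, and from 510 + w to 570, after randomization. A single window valid for every wait of 0 to 30 days is days 365–395 and 540–570, which is 31 days long, not 61. More visits may then be out of window, which Protocol Deviations requires to be recorded.
- With randomization as origin, the wait carries no device effect. A first-event log-rank simulation (N = 388, HR 0.70 after implant only, 20,000 runs) gives power of 78.6% with no wait and 77.1%, 75.9% and 71.8% for waits of 7, 14 and 30 days. The planned multiple-event analysis will differ, so these figures are only a guide. They are a reason to keep waits short.

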Report all associated adverse events. Update the device tracking records with all products. If the device is not returned to Sunshine Heart Inc., justification must be provided in the log.

Subject Withdrawal and Study Exit

A Study Exit record shall be completed if subject is unable to or refuses to continue participation in the study. Notify the Sunshine Heart clinical support team as soon as possible upon learning of a subject withdrawal/study exit.

If the subject fails to comply with follow-up visits, the study center must make repeated attempts to contact the subject. Each attempt to contact the subject must be documented in the subject's records and in the database.

If the subject officially withdraws from the study, the investigator will document the reason for withdrawal and indicate any relationship of the withdrawal to the study or the device on the eCRF.

If a subject withdraws from the study at any time, there will be no penalty or loss of future medical care.

STATISTICAL METHODS AND DATA ANALYSIS

Analysis Population

All randomized subjects will be included in the evaluation of the primary efficacy objective. Subjects will not be allowed to cross-over. All subjects implanted with the C-Pulse System will be included in the evaluation of the primary safety objective. In the event a randomized subject does not receive the implant or does not receive the randomized therapy, the subject will be analyzed according to the randomized assignment for the primary analyses. Additional supporting analyses of the primary efficacy endpoint will be conducted (as treated and per-protocol) which exclude subjects who do not receive the randomized treatment or those with major protocol deviations. The defined analysis cohorts are:

- Intent to treat: All randomized subject irrespective of treatment actually received (primary efficacy analysis)
- As treated: All randomized subjects receiving treatment as randomized
- Per protocol: All randomized subjects without major protocol deviations

Primary Efficacy Endpoint

The primary efficacy endpoint is defined as freedom from worsening heart failure related hospitalization, LVAD implant, heart transplant, and death.

The primary efficacy endpoint includes all occurrences of worsening heart failure events and will be analyzed utilizing a multiple failure time analysis.

Hypotheses

H_0 : HR=1,

H_A : HR \neq 1,

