where HR is the hazard ratio; the ratio of the C-Pulse treatment group worsening heart failure event hazard relative to the Control group worsening heart failure event hazard. This is designed to demonstrate that C-Pulse[®] therapy increases the freedom from worsening heart failure events as compared to Control as evidenced by a HR that is less than 1 and the upper bound of the two-sided 95% confidence interval for the HR excludes 1. All occurrences of worsening heart failure events will be included in the primary endpoint analysis. Details of the analysis methods can be found in the Statistical Analysis Plan.

Primary Efficacy Endpoint Sample Size

Sample size was estimated using SAS v9.2 software under two sided test for a difference in freedom from worsening heart failure. For the purposes of sample size estimation, a time to first event analysis was used to provide a conservative estimate of the required number of events and subjects. The minimum required sample size and total number of worsening heart failure events was calculated under the following assumptions:

- Significance level = 0.05
- Power = 0.80
- Proportion for 6 month freedom from worsening heart failure event in Control group = 0.72
- Underlying treatment effect on the hazard ratio scale: HR = 0.70
- Accrual time of 2.5 years
- Minimum follow-up of 12 months
- 10% Attrition per year
- 1:1 allocation ratio

Under the above assumptions a total of 265 subjects with at least one worsening heart failure events are required to be observed to ensure adequate power which indicates a total of 388 subjects randomized. As the primary analysis will include all worsening heart failure events in a multiple event analysis, the power for the detection of a difference in freedom from worsening heart failure event may be greater than 80%.

Justification for Primary Efficacy Endpoint Sample Size Assumptions

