There is no published study using the same endpoint in a similar heart failure treatment population. The MEDAMACS study has an enrollment population similar to the target population for the C-Pulse System Pivotal Trial and has an endpoint close to the C-Pulse System primary endpoint except that all-cause mortality is included. The study reports a 6-month survival free from LVAD implant, heart transplant or inotrope use of 64%. As this likely represents a higher event probability than the C-Pulse System primary endpoint, a higher freedom from event at 6 months was calculated assuming half the mortality events were not due to worsening heart failure. As the 6 month freedom from all-cause mortality estimate was 84%, an estimate for freedom from worsening heart failure event of 72% is chosen for the Control group estimate. The current proposed study was therefore powered to detect a 30% reduction in the probability of worsening heart failure event (an assumed hazard ratio of 0.70). The C-Pulse System Feasibility Study has an estimated freedom from worsening heart failure event of 95.0% at 6 months and 72.4% at 12 months, however, as this is based on 20 subjects the confidence limits of the estimate are wide and it is therefore not a desirable estimate on which to entirely base the sample size assumptions.

The study is powered to detect a statistically significant difference in freedom from worsening heart failure events favoring Treatment over Control. Worsening heart failure events represent an objective measure of worsening heart failure and an observed reduction would represent a clinically significant and meaningful improvement in heart failure subjects' health. The planned secondary analyses will provide supporting evidence of superiority in the improvement of QOL and other clinical parameters demonstrating the effectiveness of C-Pulse therapy in relieving heart failure related symptoms and associated morbidity.

Primary Safety Endpoint

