1. If the test statistic for the primary endpoint crosses the futility threshold, the DSMB may recommend that enrollment be discontinued for futility.
2. If the test statistic for the primary endpoint crosses the efficacy threshold the DSMB may make one of the following recommendations:
 - A. recommend that the trial be stopped for efficacy
 - B. recommend that the control arm be dropped as the enrollment of the treatment arm continues in order to achieve a minimum of 12 months of follow-up on a defined number of implanted subjects
 - C. recommend that the trial continues as planned to obtain a better precision on the treatment effect.
3. If neither the futility nor the efficacy boundaries are crossed, the DSMB may recommend that trial enrollment and follow-up continue as planned.

Secondary Efficacy Endpoints

The following secondary endpoints will be analyzed according to the objectives and hypothesis tests given below. Testing of the hypothesis driven secondary efficacy objectives will be conducted only in the event the primary efficacy objective and primary safety objectives are met, thereby preserving an overall Type I error rate of 5%. The secondary efficacy endpoints and associated analyses are described below:

1. Improvement in 6 Minute Hall Walk at 12 months

The improvement in 6 Minute Hall Walk will be computed as the difference between the baseline and follow-up value at 12 months. Subjects not evaluated at 12 months due to prior VAD implant, heart transplant or death will have the worst possible outcome imputed for improvement. Subjects unable to perform the 6MHW will have a value of 0 for the 12 month result. Improvement at 12 months will be compared between treatment groups under the following hypotheses.

Hypotheses

$$H_0: DT = D_c$$

$$H_A: DT \neq D_c,$$

where DT represents the distribution of improvement in 6MHW for the Treatment and D_c the distribution of improvement in 6MHW for Control. Details of the analysis methods can be found in the Statistical Analysis Plan.

2. Improvement in 6 Minute Hall Walk at 18 months

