The total days alive and out of hospital following randomization through 12 months will be computed for each subject. Each subject will contribute a maximum of 365 days alive and outside of hospital following randomization. Days the subject is in hospital will be subtracted from the maximum. For subjects with a death or study exit prior to 12 months, the days from the date of death or study exit to the date at 365 days post randomization will be subtracted from the total. The treatment groups will be compared under the following hypotheses.

Hypotheses:

$$H_0: DT = D_c$$

$$H_A: DT \neq D_c,$$

where DT represents the distribution of days alive and out of hospital for Treatment and D_c the distribution of days alive and out of hospital for Control. Details of the analysis methods can be found in the Statistical Analysis Plan.

6. Improvement in KCCQ Score at 12 months

The improvement in overall KCCQ score will be computed as the difference between the baseline and follow-up scores at 12 months. Subjects not evaluated at 12 months due to prior VAD implant, heart transplant or death will have the worst possible outcome imputed for improvement. Improvement at 12 months will be compared between treatment groups under the following hypotheses.

Hypotheses

$$H_0: DT = Dc$$

$$H_A: DT \neq Dc,$$

where DT represents the distribution of improvement in Overall KCCQ Score for Treatment and Dc the distribution of improvement in Overall KCCQ for Control. Details of the analysis methods can be found in the Statistical Analysis Plan.

Additional Supportive Analyses

1. Components of primary efficacy endpoint

The components of the primary endpoint will be summarized individually by treatment group. The proportions of subjects with heart failure related hospitalization, LVAD implant, heart transplant, and death due to worsening heart failure will be reported and the time to each event will be described by Kaplan-Meier curves. The number and proportion of subjects with hospitalization due to worsening heart failure as well as the rate per patient year will be summarized.

2. All-cause mortality

All-cause mortality will be summarized by treatment group by number and percent of subjects as well as by Kaplan-Meier curves.

3. Major cardiac events

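### LVAD implant and heart transplant are primary efficacy events by definition, yet the Data Collection Overview censors those subjects and no text says the event is counted first

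*Combined protocol and SAP*

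**What the plan says.** Three places treat LVAD implant and heart transplant as primary efficacy events.

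- **Objectives, Primary Efficacy Objective:** the aim is superiority in "survival free from worsening heart failure resulting in hospitalization, LVAD implantation, cardiac transplantation or death as compared to OMT".
- **Statistical Methods, Primary Efficacy Endpoint:** "The primary efficacy endpoint is defined as freedom from worsening heart failure related hospitalization, LVAD implant, heart transplant, and death". All occurrences of worsening heart failure events enter a multiple failure time analysis.
- **Additional Supportive Analyses, item 1 (components of the primary endpoint):** "The proportions of subjects with heart failure related hospitalization, LVAD implant, heart transplant, and death due to worsening heart failure will be reported", with Kaplan-Meier curves for each.

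One place says something different. Under Procedures, Data Collection Overview: "If the subjects are transplanted or placed on another device they will be censored from the primary endpoint analysis and study exited".

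The statistical section has its own censoring rule, under Handling of Missing Data. It names loss to follow-up and explant, censored at the last assessment, and does not mention LVAD or transplant. For methods, the Hypotheses text refers elsewhere: "Details of the analysis methods can be found in the Statistical Analysis Plan".

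**The concern.** A subject cannot both have a component event at LVAD implant or transplant and be censored there as event-free. Under the literal rule, a subject whose first qualifying event is an LVAD or transplant contributes no event. Censoring would then be triggered by the failure that the endpoint is meant to capture, so it would be informative, and the estimated hazard ratio would belong to a narrower endpoint than the one defined.

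This decides what counts as an event in the primary analysis of a trial meant to support marketing approval. The Interim Analysis section applies its futility and efficacy thresholds to the same events, so the rule matters there as well. If it is left open until data are seen, the choice becomes post hoc.

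**Working it through.** **1. The rules side by side**

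| Section | LVAD implant or transplant is |
|---|---|
| Primary Efficacy Objective | an event |
| Primary Efficacy Endpoint | an event |
| Additional Supportive Analyses, item 1 | a component of the endpoint |
| Handling of Missing Data, primary analysis | not named |
| Data Collection Overview | censored, then study exit |

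The contradiction rests on this comparison alone and needs no calculation.

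**2. The plan's control rate**

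The sample size justification starts from an external study: "The study reports a 6-month survival free from LVAD implant, heart transplant or inotrope use of 64" per cent. Survival at 6 months was 84%, and half of the deaths are assumed not to be due to worsening heart failure: 0.64 + 0.5 × (1 − 0.84) = 0.72, which is the plan's figure. Only deaths are removed, so LVAD and transplant remain events in the planning rate. This is supporting context. The external composite is only close to this trial's endpoint.

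**3. The plan's event count and size**

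- Inputs (Primary Efficacy Endpoint Sample Size): HR 0.70, two-sided 0.05, power 0.80, 6-month control freedom 0.72, accrual 2.5 years, minimum follow-up 1 year, 10% attrition per year, 194 per arm.
- Required events (Schoenfeld): 4 × (1.960 + 0.842)² / (ln 0.70)² = 247.
- Control hazard: −ln(0.72)/0.5 = 0.657 per year. Treated hazard: 0.7 × 0.657 = 0.460.
- Event probability with hazard λ and loss hazard η: the average of λ/(λ+η) × [1 − exp(−(λ+η)t)] for t uniform on 1 to 3.5 years.
- With η = −ln(0.9) = 0.105: 0.682 and 0.566, mean 0.624, so 247/0.624 = 396. This is within 3% of the stated 388. Expected events are 194 × (0.682 + 0.566) = 242.
- With no attrition: 0.7455 and 0.6248, giving 194 × 1.3703 = 266, close to the stated 265.

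The gap between 265 and 242 is a separate matter.

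**4. What losing events would do, by assumed share**

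Power = Φ(|ln 0.70| × √d / 2 − 1.96), with d the first events left after removing a share f. The documents give no f, so every value below is an assumption.

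| f | d from 265 | power | d from 242 | power |
|---|---|---|---|---|
| 0 | 265 | 0.827 | 242 | 0.793 |
| 5% | 252 | 0.808 | 230 | 0.772 |
| 10% | 238.5 | 0.786 | 218 | 0.749 |
| 20% | 212 | 0.738 | 194 | 0.699 |

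The table holds HR at 0.70 and treats each LVAD or transplant as the subject's first event. In the planned recurrent-event analysis, earlier heart failure hospitalizations of the same subjects would still count, so the loss could be smaller. The table shows how power depends on f. It does not measure a loss in this trial.

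**The case against.** The strongest reply is that the two rules are compatible. In a multiple failure time analysis a terminal event can be counted and risk time then ended. The censoring sentence sits in a follow-up section and pairs censoring with study exit, which suggests the end of observation. The Objectives text also says where definitions live: "Refer to the section on Statistical Methods and Data Analysis for a detailed discussion of the definitions and methodology". That section names LVAD and transplant as events and does not list them as reasons for censoring. This reading is probably the intended one. But it is not written anywhere in the text reviewed, and the sentence as it stands says these subjects are censored from the primary endpoint analysis. The reply therefore reduces the point to a conflict that must be reconciled. It does not remove it.

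A reader might also infer more than the documents support:

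- **That the events will be dropped.** The Statistical Analysis Plan was not available, and it may already state the count-then-stop rule.
- **That the secondary endpoints add a second contradiction.** For the 12-month walk test the plan says "Subjects not evaluated at 12 months due to prior VAD implant, heart transplant or death will have the worst possible outcome imputed for improvement". That treats these subjects as failures, but it governs a secondary endpoint and not primary censoring.
- **That the bias favours the device.** Only treated subjects can be explanted, and Appendix K recommends C-Pulse removal at LVAD placement or transplant, so the explant censoring rule could seem to catch treated cases only. However, the next paragraph of Handling of Missing Data lists LVAD, transplant and explant separately, so explant there probably excludes them. The Data Collection Overview sentence itself applies to both arms.
- **That most events would be lost.** On the planning arithmetic, 36 − 16 = 20 of the 36 − 8 = 28 percentage points (71%) are LVAD, transplant or inotrope use. That figure has no split, includes inotrope use and comes from a composite that does not list heart failure hospitalization. It says nothing usable about the share in this trial.

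**Conclusion.** The conflict is real and is in current text. Three sections count LVAD implant and transplant as primary efficacy events, one censors them, and no text reviewed reconciles the two. It should be fixed before the interim analysis because it defines the primary event. The conclusion rests on the wording alone and is conditional on the Statistical Analysis Plan, which may already settle it.

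The size is not determinable. Bias could go either way, and the power loss depends on a share that the documents do not give.

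Two neighbouring questions stay open and are not decided here. One is whether death in the primary endpoint means all-cause or heart failure death. The other is whether an LVAD or transplant must result from worsening heart failure, as the objective suggests and the endpoint definition does not say.

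**What to change.** Replace the censoring sentence in the Data Collection Overview with:

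> *An LVAD implant or heart transplant that meets the definition under Primary Efficacy Endpoint is counted as a primary endpoint event on its date; the subject's risk period for further primary events ends on that date and the subject is then study exited. Subjects placed on another device that is not an endpoint component are censored on the date of that device.*

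Add to Handling of Missing Data:

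> *Explant at or for an LVAD implant or heart transplant is handled as that event and not as censoring at the last assessment.*

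Then check that the Statistical Analysis Plan says the same.

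The replacement keeps the study exit instruction and a rule for other devices. Tying the event to the endpoint definition leaves the two open questions for separate decisions, and censoring after explant for other reasons is also left as it is.

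The cost is one sentence replaced by two, one sentence added and one document check. No new data or analysis are needed, since the supportive analyses already report LVAD and transplant by arm with time to each event. If count-then-stop was always intended, the edit only records it, and 265 events and 388 subjects stand as planned.
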